3.7.19 Laboratory Evaluations

Hematology assessments will include a leukocyte count with differential (neutrophils, eosinophils, lymphocytes, monocytes, and basophils), erythrocytes, hematocrit, hemoglobin, and platelet count. Clinical blood chemistry laboratory analytes will include electrolytes (sodium, potassium, chloride, and bicarbonate), blood urea nitrogen, serum creatinine, glucose, total bilirubin, aspartate aminotransferase, alanine aminotransferase, alkaline phosphatase, lactate dehydrogenase, uric acid, total protein, albumin, calcium, magnesium, and phosphateTesting will be performed at the central lab,

Pregnancy testing is required for all female participants of childbearing potential. It will include a serum pregnancy test at Screening and a urine pregnancy test at all subsequent visits during the Treatment and Safety Extension Phases.

[figure not shown]
3.7.20 Pharmacokinetic testing

Blood samples for assessment of plasma PK will be collected from approximately 30 randomized and successfully enrolled participants at participating US sites. At the Day 1 visit, the blood sample for plasma PK analysis will be collected before the LYR-210 administration/sham procedure. Subsequent blood samples (at Weeks 8, 16, 20, and 24) may be collected at any time of the day during the scheduled study visits. The concentration of MF in plasma will be

measured at a central core lab using a validated liquid chromatography-mass spectrometry (LC-MS) method.

[figure not shown]

PAGE 40 OF 99

PROPRIETARY AND CONFIDENTIAL

5. Investigational Product Information

5.1 Investigational product description

The LYR-210 System is a combination product comprised of a single-use applicator, preloaded with an anti-inflammatory drug matrix. LYR-210 contains mometasone furoate (MF), an active ingredient in multiple FDA-approved products indicated for therapeutic and prophylactic management of seasonal and perennial allergic rhinitis (AR), nasal polyps, a phenotype of CRS disease, and asthma. LYR-210 is designed to gradually soften over time and is made of bioabsorbable polymers that have been used as components of approved pharmaceutical drugs and/or medical devices.

Each LYR-210 contains a total MF dose of 7500 μg. LYR-210 is intended to be administered bilaterally into the middle meatus by an otolaryngologist under endoscopic visualization using

the provided single-use applicator. Once administered, each LYR-210 is designed to gradually deliver sustained doses of MF to the inflamed mucosal tissue over a 24-week resident time. Bilateral placement of LYR-210 is designed to deliver a total dose of 15,000 μ g MF over the 24 weeks, or an average daily dose of 89 μ g MF per human participant (or approximately 45 μ g MF per nostril).

5.2 Investigational product management

The sponsor will supply quantities of LYR-210 and the sham procedure articles sufficient to allow completion of the study. The investigator or designee must maintain accurate records to document the disposition of all products received by the clinical site. Required information includes the kit numbers received, date received, date used, product description, and a participant identifier for product that has been administered. Investigational sites will use a form to document product disposition, which will be reviewed by the study monitor during routine monitoring visits. When all study procedures are complete, any unused investigational product will be returned to sponsor or discarded per sponsor authorization along with a final accountability log. The accountability log must document the disposition of all investigational product, including those that have been returned to the sponsor.

5.3 Product return

All drug matrices administered to a participant are to be removed, as indicated in the Schedule of Assessments (**Appendix 14.1**). All study product not administered to a participant must be returned to the sponsor or designee or discarded per sponsor authorization. Applicators successfully used for administration may be disposed on site after the study procedure is complete.

The investigator will inform the sponsor of any complaints or malfunctions during the study. The sponsor will investigate all product complaints and malfunctions.

Instructions for returning product will be provided to the sites by the sponsor.

5.4 Packaging, labeling, and storage

The investigational products (LYR-210 and Sham) will be packaged and labeled, as required by regional legislation and industry guidelines. The LYR-210 System and the Sham product are individually packaged in a foil pouch which is sterilized and placed within a shelf carton.

The investigational products should be kept in a locked storage and stored in the original packaging to protect from moisture and light and at controlled room temperature (15 °C to 25 °C [59 °F to 77 °F]), with excursions permitted up to 30 °C (86 °F, inclusive).

The sponsor or designee will ship study products to the sites as needed. Specific instructions for ordering product will be provided to the sites. Traceability of LYR-210 or the sham procedure articles will be achieved by assigning each matrix and applicator a unique kit number.

6. Monitoring Procedures

Sponsor personnel or qualified designees will monitor the clinical study in a manner consistent with 21 CFR 312, Subpart D, Responsibilities of Sponsors and Investigators, and other applicable local or national regulations. Specific monitor contact information will be provided separately from the protocol.

6.1 Investigational site monitoring

An appropriate representative of the sponsor or designee (study monitor) will verify participant data and ensure compliance with GCP, clinical protocol, and other study requirements, according to the guidelines set forth in the monitoring standard operating procedures (SOPs) and applicable regulatory requirements. The study monitor will ensure the investigator continues to have appropriate staff and facilities to conduct the clinical study safely and effectively. Monitoring will be performed in accordance with a prespecified monitoring plan that is in compliance with applicable SOPs. Upon reasonable notice, the investigator and institution agree to provide the sponsor representatives or designees and applicable regulatory authorities with direct access to source documents relevant to the study for sponsor quality assurance audits or inspections by the regulatory authorities.

Completed CRFs will be verified by the study monitor at the investigational sites at regular intervals throughout the study. The investigator will allow the monitor and/or representative of the sponsor, and any regulatory body to review and inspect the study files, participant CRFs, participant medical records and other study-related documents, as required.

All CRFs will be reviewed for completeness and clarity. Missing or unclear data will be investigated by the study monitor and will be retrieved, clarified, and completed by study personnel as necessary throughout the study. The sponsor or their authorized representative may request additional documentation from the investigator such as physician procedure notes or physician written summaries when AEs are observed and reported.

6.2 Investigators

The sponsor will select investigators with appropriate training and experience to participate in this clinical study. Sites will be selected based upon the qualifications of the principal investigator at the site as well as other parameters, including proven ability and infrastructure to

perform clinical studies. The complete list of all site investigators and the relevant clinical sites will be maintained within the sponsor's trial master file (TMF).

In addition to specific training relating to use of the investigational product, the training of the investigator and appropriate clinical site personnel will be the responsibility of the sponsor (or designee) and may be conducted during an investigator meeting, a site initiation visit, or other appropriate venue. Training will include, but not be limited to, the clinical protocol, IB, CRF completion, GCP, and clinical study personnel responsibilities. All training will be documented prior to engaging in study-related activities.

7. Adverse Event Definitions and Reporting

7.1 Adverse events and treatment-emergent adverse events

An AE is any untoward medical occurrence (signs, symptoms, abnormal laboratory findings) in a participant regardless of relationship to the investigational product or procedure. Each AE is either expected or unexpected as described below. The site is required to report Aes that occur during the study. These events shall also be classified according to the suspected causality by the study investigator.

Throughout the course of the study, all efforts will be made to remain alert to possible Aes or untoward findings. If AEs occur, the first concern will be the safety and welfare of the participant. Appropriate medical intervention will be undertaken. Any AE observed by the investigator or reported by the participants, whether or not ascribed to the investigational procedure or product, will be recorded on the participant's AE case report form (CRF). A new AE CRF will be used for each AE. All on-going AEs that result in early termination (ET) from the study or are deemed to be study product- or procedure-related by the site investigator will be followed until resolution or stabilization of the AE.

Documentation regarding the AE should be made as to the nature, date of onset, end date, severity, and relationship to study product, action(s) taken, seriousness, and outcome of any sign or symptom observed by the physician or reported by the participant upon indirect questioning.

A treatment emergent AE (TEAE) is an AE that occurs or worsens on or after initiation of the LYR-210 administration/sham procedure.

7.2 Serious adverse events

An AE or adverse reaction is considered a serious adverse event (SAE) if, in the view of either the investigator or sponsor, it results in any of the following outcomes:

- Death
- A life-threatening AE (Note: an AE or adverse reaction is considered "life-threatening" if, in view of either the investigator or sponsor, its occurrence places the participant at immediate risk of death. It does not include an event that, had it occurred in a more severe form, might have caused death.)
- Requires hospitalization or prolongation of existing hospitalizations (Note: any hospital admission with at least 1 overnight stay will be considered an inpatient hospitalization. An emergency room or urgent care visit without hospital admission will not be recorded as an SAE under this criterion, nor will hospitalization for a procedure scheduled or planned before signing of informed consent, or elective treatment of a pre-existing condition that did not worsen from baseline. However, unexpected complications and/or prolongation of hospitalization that occur during elective surgery should be recorded as AEs and assessed for seriousness. Admission to the hospital for social or situational reasons, eg, no place to stay, live too far away to come for hospital visits, respite care, will not be considered inpatient hospitalization.)
- A persistent or significant disability/incapacity or substantial disruption of the ability to conduct normal life functions
- A congenital anomaly/birth defect
- An important medical event (Note: important medical events that do not meet any of the above criteria may be considered an SAE when, based upon appropriate medical judgment, they may jeopardize the participant and may require medical or surgical intervention to prevent one of the outcomes listed above [eg, anaphylaxis]).

The investigator will assess each AE for its seriousness. Please note the term "serious" AE is not synonymous with a "severe" AE, which may be used to describe the intensity of an event experienced by the participant (Section 7.4). Any treatment-related SAE (Section 7.3) will be followed until resolution of the event, or until the participant withdraws from the study.

- 7.3 Relationship to investigational product or study procedure
 The relationship between an AE and the LYR-210 study drug product or LYR-210
 administration/sham procedure (within 24 hours) will be determined by the investigator based on his or her clinical judgment and the following definitions:
 - **Definitely related:** The AE follows a reasonable temporal sequence from administration of the investigational product or the study procedure and the AE follows a known or expected response pattern to the investigational product or study procedure.

- **Probably related:** The AE follows a reasonable temporal sequence from administration of the investigational product or the study procedure and is unlikely to have been produced by other factors (eg, disease, concomitant medications).
- Possibly related: The AE follows a reasonable temporal sequence from administration of the investigational product or the study procedure and the AE follows a known or expected response pattern to the investigational product or study procedure but could readily have been produced by several other factors.
- Unlikely related: The AE is temporally distant from administration of the investigational product or the study procedure that makes a relationship improbable and the AE could readily have been produced by several other factors.
- Not related: An AE for which sufficient information exists to indicate that the etiology is unrelated to the investigational product or study procedure. One or more of the following variables apply:
 - o The AE does not follow a reasonable temporal sequence following administration of the investigational product or study procedure
 - o The AE is readily explained by the participant's clinical state or other therapies

The following factors should be considered when evaluating relatedness:

- The temporal sequence from study drug administration the event should occur after the study drug is given. The length of time from study drug exposure to event should be evaluated in the clinical context of the event.
- Underlying, concomitant, intercurrent diseases each report should be evaluated in the context of the natural history and course of the disease being treated and any other disease the participant may have.
- Concomitant drug the other drugs the participant is taking or the treatment the participant receives should be examined to determine whether any of them might be recognized to cause the event in question.
- Known response pattern for this class of study drug clinical and/or preclinical data may indicate whether a particular response is likely to be a class effect.
- Exposure to physical and/or mental stresses the exposure to stress might induce adverse changes in the participant and provide a logical and better explanation for the event.
- The pharmacology and pharmacokinetics of the study drug the known pharmacologic properties (absorption, distribution, metabolism, and excretion) of the study drug should be considered.

7.4 Severity of adverse events

Severity of an AE is defined as a qualitative assessment of the degree of intensity of an AE as determined by the investigator or reported to him/her by the participant. The assessment of severity is made irrespective of relationship to study procedure or product or seriousness of the event and should be evaluated according to the following scale:

- Mild: Event is noticeable to the participant but is easily tolerated and does not interfere with the participant's daily activities.
- Moderate: Event is bothersome, possibly requiring additional therapy, and may interfere with the participant's daily activities.
- Severe: Event is intolerable, necessitates additional therapy or alteration of therapy, and interferes with the participant's daily activities.

7.5 Expectedness of serious adverse events

The expectedness of a product or procedure-related SAE should be determined by sponsor based upon existing safety information about the investigational product or study procedure using these explanations:

- Unexpected: An SAE that is not listed in the study protocol, investigator's brochure (IB), or prescribing information for the registered formulation of MF or is not listed at the specificity or severity that has been observed.
- Expected: An SAE that is listed in the IB or prescribing information for the registered formulation of MF or is listed at the specificity and severity that has been observed.

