3.5.7 Clinic follow-up visits

All participants will return to clinic for the scheduled follow up assessments at Weeks 8, 16, 20, 32, 40, 44, and 48. The end of study visit at Week 52 can be conducted as an in-office visit or over the phone. Assessments at these visits include a urine pregnancy test for women of childbearing potential, COVID-19 test, nasal endoscopy, 4CS, SNOT-22, concomitant medications/procedures, and AEs. PGIS will also be assessed at Week 8 and 16 visits. Plasma for PK testing will be collected for the previously selected 30 participants. Ocular examinations are required at Weeks 8, 16, 32, 40, and 48.

At the Week 20 and Week 44 visits, after the visit assessments, all participants will undergo a LYR-210 removal or sham removal procedure. Participants who receive LYR-210 will have bilateral matrix removal using standard surgical tools. Control participants will undergo a sham removal procedure to remain blinded.

If **spontaneous dislodgement of LYR-210** occurs before the scheduled Week 20 or Week 44 visit in participants who receive LYR-210, participants are required to call the study clinic immediately to report the event. If a participant experiences dislodgement of 1 LYR-210 matrix, the participant will continue in the treatment phase. Any participant who undergoes a dual dislodgement is required to complete the assessments scheduled for the Week 20/ET visit, and subsequently the Week 24/End of Treatment Phase (EOTP) visit within 25-31 days of the ET visit. Participants with dual dislodgement can be re-randomized in the extension phase.

Opacification of ethmoid sinuses will be assessed by CT scans obtained during screening (or using a historical CT scan taken within 1 month of screening) and within 7-14 days after Week 20/ET visit, unless medically contraindicated. Participants will be instructed to stop use of saline rinse approximately 24 hours prior to the scheduled sinus CT. Daily saline irrigation should then continue following the sinus CT. If a participant is experiencing or recovering from a cold, acute exacerbation of nasal allergy, or URTI at the timing of follow up CT, the CT should be performed 4 weeks after resolution of the AE. If a participant requires SCS or sinonasal surgery as rescue treatment, the follow-up CT should be performed before receiving the rescue treatment.

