7.9 Expedited reporting

Any serious and unexpected suspected adverse reactions (SUSARs) and unexpected adverse device effect (UADE) will be reported by the sponsor or designee to the appropriate regulatory authorities in accordance with applicable local guidelines.

The SUSARs meet all the following criteria:

- Suspected adverse reaction
- Serious
- Unexpected
- Assessed as related to study treatment

A UADE is any serious adverse effect on health or safety, any life-threatening problem or death caused by, or associated with a device, if that effect, problem, or death was not previously identified in nature, severity, or degree of incidence in the application; or any other unanticipated serious problem associated with a device that relates to the rights, safety, or welfare of participants.

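### Protocol 7.5 lets a listed but worse-than-listed SAE be both Expected and Unexpected, and 7.3 leaves a gap in relatedness and an ambiguity over the removal procedure

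*Protocol*

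**What the plan says.** **Expectedness (Protocol 7.5).** The sponsor judges expectedness for product- or procedure-related SAEs.
- Expected: listing in the IB is enough. The definition then adds, as further alternatives, "prescribing information for the registered formulation of MF or is listed at the specificity and severity that has been observed".
- Unexpected, first branch: "An SAE that is not listed in the study protocol, investigator's brochure (IB), or prescribing information for the registered formulation of MF".
- Unexpected, second branch, for events that do appear in a reference document: "or is not listed at the specificity or severity that has been observed".

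The protocol is a reference document under Unexpected only.

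**Expedited reporting (Protocol 7.9).** A SUSAR must meet every listed criterion. These include being unexpected and "Assessed as related to study treatment". A UADE has a separate definition with its own test of nature, severity and incidence.

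**Relatedness (Protocol 7.3).** The relationship of an AE to the drug product or to the LYR-210 "administration/sham procedure (within 24 hours) will be determined by the investigator based on his or her clinical judgment". Possibly related requires plausible timing and that the event "follows a known or expected response pattern to the investigational product or study procedure but could readily have been produced by several other factors".

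**Removal (Protocol 3.5.7).** At Weeks 20 and 44 every participant has a removal or sham removal. "Participants who receive LYR-210 will have bilateral matrix removal using standard surgical tools". The title of protocol Table 2 names the removal procedure as a source of expected adverse events.

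**SAP 3.6.1.** The AE overview counts TEAEs related to study procedure. It does not define the procedure and sets no time limit.

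**The concern.** Relatedness and expectedness decide whether a serious reaction is handled as a SUSAR. If one SAE satisfies two opposite definitions, two assessors can apply the protocol correctly and reach different reporting decisions. A serious reaction worse than anything listed is one that expedited reporting should pick up.

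If a reaction fits none of the related categories, the investigator has no rule for calling it related. An unrelated SAE is not assessed for expectedness under 7.5 at all.

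If sites differ on whether removal is a study procedure, the SAP count of procedure-related TEAEs could be incomplete. Follow-up could also vary, because 7.1 ties follow-up of ongoing AEs to resolution or stabilization partly to whether they are judged product- or procedure-related.

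**Working it through.** No sample-size, power or error-rate figure is involved. The check is to run each type of event through the definitions.

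**Step 1. Expectedness (7.5).**

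| Where the SAE is listed | Form observed | Meets Expected? | Meets Unexpected? |
|---|---|---|---|
| IB or MF label | As listed | Yes | No |
| IB or MF label | Worse or more specific than listed | Yes, first branch | Yes, second branch |
| Nowhere | Any | No | Yes |
| Protocol only | As listed | Only if the second branch, which names no document, covers the protocol | No |
| Protocol only | Worse or more specific than listed | No | Yes |

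Row 2 is a contradiction. Row 4 depends on how the second branch of Expected is read.

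**Step 2. Test the one-word repair.** If *or* becomes *and* in Expected, row 2 becomes Unexpected only. Row 4 then meets neither definition: the SAE is not in the IB or label, yet it is listed in the protocol as observed. The reference documents must therefore be aligned in the same edit.

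**Step 3. Relatedness (7.3), given plausible timing.**

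| Known or expected pattern? | Competing cause? | Category available |
|---|---|---|
| Yes | No | Definitely or Probably |
| Yes | Yes | At least Possibly |
| No | No | Probably (needs no pattern) |
| No | Yes | No related category |

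In the last row, Definitely and Possibly fail on the pattern and Probably fails on the competing cause. Unlikely fails because the event is not remote in time. Not related requires enough information to show that the cause lies elsewhere, and a merely possible competing cause does not supply that. The event is unassigned and falls to judgment.

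**Step 4. Removal.** The Week 20 visit is Day 141±3, so removal falls about 141 − 1 = 140 days after insertion. It is neither named in the lead sentence of 7.3 nor within 24 hours of the procedure that is named. The category texts, however, say study procedure without restriction. The two can be read differently.

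**Step 5. How many removals the ambiguity touches.** Inputs are about 180 participants at 2:1 (Protocol 3.1) and the extension design (Protocol 3.5.9).
- Week 20: 180 × 2/3 = 120 LYR-210 participants.
- Week 44: 60 crossover + 120/2 = 60 re-treated, giving 120.

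These are upper bounds on participants having a matrix removal. They assume that everyone continues and no matrix dislodges. They do not count misclassified events. Only the Week 20 removals fall under this SAP, because SAP 4.2 sends the 52-week data to a separate plan.

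**The case against.** The best defence is that the safety net does not hang on these sentences. Protocol 7.7.1 sends every SAE to the sponsor within 24 hours, whatever its classification. The sponsor can apply the Unexpected branch to a worse-than-listed event, and 7.9 refers to applicable local guidelines. The UADE route does not use the 7.5 wording, and 7.10 sets up medical review of serious and nonserious AEs. In the SAP, all TEAEs, the AESIs of mucosal injury and epistaxis, and endoscopic findings at Weeks 20 and 24 are summarized by arm regardless of relatedness. All of this stands. It limits the harm, but it does not tell the sponsor which of two conflicting definitions governs.

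A reader might also infer more than the documents support:
- *That a protocol-only SAE meets neither definition.* As written, the second branch of Expected can cover it when it is seen as listed, and Unexpected covers it when it is worse.
- *That every new reaction with a competing cause is forced into Not related.* That category needs positive information that the cause lies elsewhere. 7.3 also directs the investigator to class effects and pharmacology, so an unlisted reaction may still follow an expected pattern.
- *That first-of-kind SAEs can be called expected.* An SAE listed nowhere is Unexpected only.
- *That about 240 removals have no causality assessment, or that the SAP count misses removal.* The categories in 7.3 refer to study procedure generally, 7.6 requires evaluation for complications of the study procedure, and SAP 3.6.1 has no administration-only or 24-hour limit. The body of Table 2 is not in the public text, and its absence is not held against the plan.

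**Conclusion.** The contradiction in 7.5 is real and follows from the text alone. It affects every SAE that is listed in the IB or MF label but observed in a more severe or more specific form, and it sits on a SUSAR criterion.

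The other two points are real but smaller. The relatedness gap is confined to reactions with plausible timing, a competing cause and no known or class pattern. The removal point is an ambiguity: the SAP count could be incomplete if sites read 7.3 narrowly, but the documents do not show that they will.

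The size in events is unknown because no SAE rate is given. The wording should be corrected because it governs safety reporting and the correction is cheap. Nothing here affects the efficacy analysis.

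**What to change.** 1. **Protocol 7.5.** In the Expected definition, replace the *or* before the specificity-and-severity condition with *and*. In the same edit, name identical reference documents under Expected and Unexpected.
2. **Protocol 7.3.** Remove the known-or-expected-pattern condition from Possibly related. It can stay in Definitely related.
3. **Protocol 7.3.** Define study procedure once as administration, removal and the sham counterpart of each. State that 24 hours is a guide to timing and not a limit on attribution.
4. **SAP 3.6.1.** Use that definition for TEAEs related to study procedure.

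The cost is a short protocol clarification, a matching line in the SAP and updated CRF completion guidance. No visits or assessments are added. The downside is that a few more events may be classed as related or expedited.
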